## 8 STATISTICAL CONSIDERATIONS

The primary objective of this study is to assess whether use of GI-6207 is able to result in reductions of the growth rates of tumors in patients with MTC. The changes in growth rates will be compared between two arms with either initial assignment to vaccine or surveillance, as well as secondarily determining if there is a significant change within the arm that initially receives surveillance followed by 6 months of vaccine.

Prior to randomization, patients will be stratified according to whether they were noted to have a calcitonin doubling time of <24 months vs. >24 months at baseline.

The primary endpoint will be the change from baseline to 6 months of the growth rate parameter. With 17 total patients per arm (34 total), with complete measurements of this main parameter at baseline and at 6 months after randomization, there would be 80% power to detect a difference between the two groups with respect to a change from baseline to 6 months equal to 1.0 standard deviations of the change (1.0 effect size) using a two-tailed 0.05 level two-sample t-test. In practice, if the differences from baseline to 6 months are not normally distributed on both arms (that is, if  $p < 0.05$  by a Shapiro Wilks test) then a Wilcoxon rank sum test will be performed instead.

As an important secondary objective, using the surveillance arm, two related secondary endpoints will be explored, both the actual magnitude of the change in the growth rate parameter as well as the fraction who exhibit a substantial, 50% decline in the growth rate as a result of treatment.

For the 17 patients will be enrolled on the surveillance arm, the growth rate determined at 12 months (after 6 months of vaccine) will be subtracted from that obtained at 6 months (after surveillance) to determine the actual change in the growth rate for receiving vaccine after 6 months of surveillance. With 17 patients, there is 82% power to detect a difference in the values at the two time points equal to  $\frac{3}{4}$  of the SD of the change (.75 effect size) assuming that a two-tailed 0.05 alpha level paired t-test is used.

Also, as an additional secondary exploration, using all 17 patients on the surveillance arm, the fraction that experiences a 50% decline relative to the time of starting vaccine will be determined. Using an exact binomial test, 17 patients will have 83% power to test whether the fraction exceeds a null fraction of 20% and is consistent with 50% who have 50% declines, with a one-tailed 0.05 alpha level test. In practice, the fraction with a 50% decline will have a 95% confidence interval created about the result in order to describe what values it would be consistent with.

Exploratory analyses will also be performed to compare the growth rate changes at additional time points, such as 7, 10 and 12 months.

It is expected that the trial will accrue approximately 1-2 patients per month may be accrued; thus it is expected that this study may enroll 34 evaluable patients within 24-30 months. To allow for the possibility of a rare inevaluable patient, the accrual ceiling will be set at 37.

**Abbreviated Title:** GI-6207 in MTC

**NantCell Study Number:** QUILT-3.006

**NCI Protocol #:** 13-C-0095

**OSP#:** 1301-1199

**Version Date:** May 14, 2018

**IBC#:** RD-13-I-10

**Amendment:** G

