## Schema

- All patients enrolled will have evaluable disease
- Consistent with phase 1 study dosing, all patients will be given GI-6207 every 2 weeks for 3 months and then monthly. Dose = 40/YU.
- Half of the patients will be on surveillance for 6 months to determine a growth rate for comparison to those who start GI-6207 immediately
- The primary endpoint will compare the calcitonin growth rate in the GI-6207 arm at 6 months, with patients on the surveillance arm at 6 months.
- A secondary endpoint will compare the surveillance arm growth rate after 6 months of GI-6207 to each patient's own baseline growth rate determined after 6 months of surveillance.
- Patients will be evaluated with radiographic imaging at enrollment and every 3 months while on study
- Patients will be removed from treatment if there is clinical progression or radiographic progression (based on the immune-related response criteria) while on GI-6207 treatment
- Patients will be stratified based on pre-treatment doubling time of less than or greater than 24 months.
- Once patients have completed one year of therapy with GI-6207, patients without radiographic progression will have the option to receive vaccine every 3 months for an additional 12 months. Patients who remain on vaccine will continue to be scanned every 3 months.

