## Schema

- All patients enrolled will have evaluable disease
- Consistent with phase I study dosing, all patients will be given GI-6207 every 2 weeks for 3 months and then monthly. Dose = 40/YU.
- Half of the patients will be on surveillance for 6 months to determine a growth rate for comparison to those who start GI-6207 immediately
- The primary endpoint will compare the calcitonin growth rate in the GI-6207 arm at 6 months, with patients on the surveillance arm at 6 months.
- A secondary endpoint will compare the surveillance arm growth rate after 6 months of GI-6207 to each patient's own baseline growth rate determined after 6 months of surveillance.
- Patients will be evaluated with radiographic imaging at enrollment and every 3 months while on study
- Patients will be removed from treatment if there is clinical progression or radiographic progression (based on the immune-related response criteria) while on GI-6207 treatment
- Patients will be stratified based on pre-treatment doubling time of less than or greater than 24 months.
- Once patients have completed one year of therapy with GI-6207, patients without radiographic progression will have the option to receive vaccine every 3 months for an additional 12 months. Patients who remain on vaccine will continue to be scanned every 3 months.

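### Does the plan need a stated rule for a randomised patient who has no 6-month growth rate?

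*Combined protocol and SAP*

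**What the plan says.** Section 8 defines the primary comparison by arm as first assigned: "The changes in growth rates will be compared between two arms with either initial assignment to vaccine or surveillance". The endpoint is a within-patient quantity: "The primary endpoint will be the change from baseline to 6 months of the growth rate parameter". The 80% power is stated for 17 patients per arm "with complete measurements of this main parameter at baseline and at 6 months after randomization", at an effect of 1.0 SD of the change and a two-sided 0.05 two-sample t-test.

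On accrual, Section 8 says "thus it is expected that this study may enroll 34 evaluable patients within 24-30 months", and then: "To allow for the possibility of a rare inevaluable patient, the accrual ceiling will be set at 37". Its only analysis contingency is a Wilcoxon rank sum test when the changes are not normally distributed. That deals with the shape of the data, not with absent values.

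The Schema says that patients will be "removed from treatment if there is clinical progression or radiographic progression (based on the immune-related response criteria) while on GI-6207 treatment". It also says: "Patients will be evaluated with radiographic imaging at enrollment and every 3 months while on study".

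**The concern.** A patient without a 6-month growth rate has no change score and cannot enter the t-test. Section 8 foresees inevaluable patients and leaves 37 - 34 = 3 spare places. Read together, this suggests that such a patient would be left out and made up by further accrual. That would restore the number analysed but not the randomised comparison.

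The Schema offers a plausible reason for loss linked to outcome. Removal for progression applies while on GI-6207, and in the first 6 months only the immediate-vaccine arm is on GI-6207. If patients with the fastest-growing disease left that arm without a month-6 value, the remaining vaccine patients would look better than they should. With 17 per arm, three patients are not negligible. Leaving evaluable undefined also leaves room to decide who counts after the data are seen.

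**Working it through.** **1. The plan's own figure.** Inputs from Section 8: n = 17 per arm, effect 1.0 SD, two-sided alpha 0.05. The noncentral t has df = 17 + 17 - 2 = 32 and noncentrality 1.0/sqrt(1/17 + 1/17) = 2.92. Power is 80.7%, so the stated 80% is correct for complete pairs.

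**2. Losing a few pairs without replacement.** The same formula gives 79.4% for 16 v 17, 78.1% for 16 v 16 and 75.3% for 15 v 15. The spare places cover 3/37 = 8.1% of those randomised.

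**3. Bias if lost patients are replaced.** The documents give no loss rate and no link between loss and outcome, so every driver here is an assumption. Model: there is no true effect. An arm of 17 + k patients loses the k with the highest progression score. The score has correlation r with the growth-rate change. The remaining 17 are compared with 17 by t-test (100,000 simulated trials per cell). Negative bias favours vaccine.

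| Lost from vaccine arm only | r = 0.3 | r = 0.5 | r = 0.7 |
|---|---|---|---|
| 1: bias (SD) / two-sided error | -0.03 / 5.2% | -0.05 / 5.5% | -0.07 / 5.9% |
| 2: bias (SD) / two-sided error | -0.06 / 5.4% | -0.10 / 6.0% | -0.13 / 7.3% |
| 3: bias (SD) / two-sided error | -0.08 / 5.7% | -0.13 / 7.0% | -0.18 / 9.1% |

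With one loss in each arm there is no bias, and the error is 5.2% to 5.8% (r = 0.3 to 0.7). With two vaccine losses and one surveillance loss, the bias is -0.02 to -0.06 SD and the error 5.2% to 6.4%. The sign reverses if the losses fall on surveillance or if r is negative. At r = 0 there is no bias.

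Here r links the score to the change; it is not the correlation between being lost and the change. A score correlation of 0.7 corresponds to a loss-change correlation of only 0.31 (one lost) to 0.43 (three lost).

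**4. What a substitute rule would cost.** Suppose all randomised patients are kept, using shortened calcitonin series for those lost from the vaccine arm, with 1 SD of extra noise in those patients. Power at a true effect of 1.0 SD is then:

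- 80% to 82% if the lost patients still show the full vaccine effect;
- about 78%, 75% and 72% for 1, 2 and 3 losses if they show half of it (score r = 0.5).

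The comparator is 80.7% for 17 v 17. Giving lost vaccine patients the worst rank leaves 67% to 72% with one loss and 36% to 51% with three.

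**5. The passages side by side.** For the feared bias to arise, four things must all happen: a patient progresses before month 6, that patient has no month-6 calcitonin rate, the patient is replaced and left out, and the losses differ by arm. The first is possible. The second does not follow from the Schema, which ends treatment, not measurement, and keeps imaging going every 3 months while on study. The third is an inference from the accrual ceiling. The fourth is unknown.

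**The case for a change.** The strongest case for acting is pre-specification. The text available has no definition of evaluable, no named analysis set and no rule for a missing 6-month rate. A few sentences would supply them and remove any suspicion that patients were classified after the fact. In the worst corner of the table, the rate of falsely favouring vaccine is 8.3% against a nominal 2.5%. The Précis reports that growth rates can be calculated within 3 months, which suggests that a shorter series could serve.

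The silence is real, and a definition of evaluable with a count of missing rates by arm would be a reasonable courtesy. The rest is weaker. The calcitonin schedule, the off-study rules and any definition of evaluability are not in the text available, and a rule would normally be found there. An inevaluable patient could as easily be one found ineligible or without a baseline rate. The Précis statement on 3 months is preliminary background, and the same list puts vaccine effects on growth rate at 3 to 4 months, so a truncated series may miss the effect it is meant to measure. Keeping all randomised patients also leaves no primary rule for someone with no usable post-baseline rate who has not progressed; worst-rank handling for progressors would not cover that patient.

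**Conclusion.** No change to the plan. Section 8 contains no error on this point: its power figure is right for its stated condition, and its comparison is already by initial assignment. What is left is a gap that an analyst would fill in the ordinary way: keep patients in their assigned arms, use the growth rates available whatever the treatment status, and report who is missing and why.

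For the rare single loss that the plan expects, the assumed-input bias is 0.03 to 0.07 SD against a planned effect of 1.0 SD, with two-sided error of 5.2% to 5.9%. Errors near 9% need all three spare places lost from one arm and a score correlation of 0.7. Neither the direction nor the size of any bias can be derived from the documents. The conclusion would change if the full protocol showed that calcitonin sampling stops when treatment stops and that such patients are replaced.

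### Randomisation is stratified by doubling time, but the primary test uses neither the stratum nor baseline growth rate as a covariate: valid, but it may give up power

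*Combined protocol and SAP*

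**What the plan says.** Section 8 (Statistical Considerations) has patients "stratified according to whether they were noted to have a calcitonin doubling time of <24 months vs. >24 months at baseline", and the Schema repeats it: "Patients will be stratified based on pre-treatment doubling time of less than or greater than 24 months".

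The same section defines the endpoint: "The primary endpoint will be the change from baseline to 6 months of the growth rate parameter". The arms are compared "using a two-tailed 0.05 level two-sample t-test". If the changes fail a Shapiro-Wilk test at 0.05, "then a Wilcoxon rank sum test will be performed instead". The design has 17 evaluable patients per arm, 80% power and a difference of 1.0 SD of the change.

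The Schema describes the primary comparison differently. It says it will "compare the calcitonin growth rate in the GI-6207 arm at 6 months, with patients on the surveillance arm at 6 months", with no mention of change.

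No part of the available text enters the stratum or the baseline growth rate as a covariate, or names a stratified test. Baseline is used only by subtraction.

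**The concern.** The design treats doubling time as important enough to balance on, and the analysis then ignores it. Two consequences follow if the stratum or the baseline value predicts change.

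- Stratified randomisation removes most between-stratum variation from the arm difference, but the unadjusted t-test leaves that variation in its standard error. The standard error is then too large and the true size falls below 5%.
- Subtracting baseline fixes its slope at 1. If the true slope is different, the change score carries noise that a fitted slope would remove.

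A link is plausible. Under exponential growth, doubling time is ln 2 divided by growth rate, so the stratum is a coarse version of baseline growth rate, and baseline is itself part of the change score. A trial of 34 patients powered only for a 1.0 SD effect has little precision to spare. Every patient counted in the power statement must already have a baseline value.

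**Working it through.** **Inputs from Section 8.** 17 per arm, effect 1.0 SD of change, two-sided alpha 0.05.

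**Step 1: reproduce the stated power.** Noncentrality = 1.0 × √(17/2) = 2.915, df = 32, critical value 2.037. Power = 0.807. With 16 per arm it is 0.781, so 17 is the smallest number reaching 80%. The plan's figure is right for the planned test.

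**Step 2: what adjustment can remove.** Assumptions, none in the documents: normal data; rho is the correlation of baseline with month-6 growth rate; k is SD at baseline divided by SD at month 6. Setting the month-6 SD to 1:

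- variance of change = 1 + k² − 2·rho·k
- variance left after regression on baseline = 1 − rho²
- true slope = rho/k

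For k = 1 the ratio of the second to the first is (1 + rho)/2. At rho = 0.5 it is 0.75, so baseline explains 25% of the variance of change. At k = 0.5 and rho = 0.5 the slope is 1, both variances are 0.75, and there is nothing to gain.

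Writing R² for the share of variance explained by the covariates, the noncentrality becomes 2.915/√(1 − R²) with df = 30. Power is 0.805 at R² = 0, 0.845 at 0.10, 0.884 at 0.20 and 0.921 at 0.30. This ignores the small loss from chance imbalance in baseline, so simulation is needed.

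**Step 3: simulation.** 40,000 trials per setting. Further assumptions: permuted blocks within strata, and the stratum taken as a median cut of baseline growth rate. Dashes mark values not reported here.

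| k | rho | t-test size | t-test power | Change + stratum power | ANCOVA power |
|---|---|---|---|---|---|
| 1 | 0.3 | 2.9% | 83.0% | 89.3% | 93.2% |
| 1 | 0.5 | 3.2% | 82.4% | 86.9% | 89.3% |
| 1 | 0.7 | 4.2% | 81.6% | 84.2% | 85.2% |
| 1 | 0.9 | 4.6% | 81.0% | 81.8% | 81.3% |
| 0.7 | 0.3 | – | 81.7% | – | 85.1% |
| 0.7 | 0.5 | – | 81.1% | – | 81.2% |
| 0.7 | 0.7 (slope 1) | – | 80.6% | – | 79.1% |
| 0.5 | 0.5 (slope 1) | – | 80.6% | 80.4% | 79.0% |

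ANCOVA here means arm, baseline and stratum; its size at k = 1 was 4.8% to 5.1%. With k = 1.4 and rho from 0.3 to 0.9, t-test power was 84.6–85.2% and ANCOVA power 97.2–98.8%. A 25/75 stratum split instead of the median changed little: at k = 1 and rho = 0.5, 82.1% against 89.2%. Independent repeats agreed to within about 1 point.

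At k = 1 the stratum alone keeps (89.3 − 83.0)/(93.2 − 83.0) = 62% of the ANCOVA gain at rho 0.3, 4.5/6.9 = 65% at 0.5 and 2.6/3.6 = 72% at 0.7.

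**Step 4: rank fallback.** 15,000 trials, normal data, k = 1, rho 0.3/0.5/0.7/0.9:

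- plain Wilcoxon: power 80.4/79.7/78.9/78.0%, size 2.7/3.4/3.8/4.4%
- van Elteren: power 86.6/83.7/81.1/77.9%, size 4.6–5.0%
- rank ANCOVA: power 91.2/86.8/80.4/71.2%

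At slope 1 (k = 0.5, rho = 0.5), Wilcoxon gave 78.3% and van Elteren 77.1%.

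**Step 5: the two wordings of the endpoint.** Take change = a + τ·arm + β·baseline + γ·stratum and add baseline to both sides. This gives month 6 = a + τ·arm + (β + 1)·baseline + γ·stratum. The arm effect τ, its standard error and its p-value are identical. Once baseline is in the model, the Schema and Section 8 describe the same test.

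**The case against.** The strongest reply is that nothing in Section 8 is wrong. Endpoint, test, alpha and sample size agree with one another, and the stated power does not rely on stratification. That stands, which makes this a recommended improvement and not a correction.

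The benefit also rests on rho and k, which the documents do not give. The range runs from a gain of 12–14 points (k = 1.4) through almost nothing (k = 1 with rho 0.9; k = 0.7 with rho 0.5) to a loss of about 1.6 points. That stands too, and it limits how firmly any gain can be promised.

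The below-nominal size needs allocation balanced within strata, and the text does not describe the allocation method. Without that balance, t-test size at k = 1 returns to 5.0%, 4.8% and 5.4% for rho 0.3, 0.5 and 0.7. Balance within strata is the ordinary meaning of stratified randomisation, and the power gain survives without it: 81.4% to 92.2% at rho 0.3, and 80.8% to 88.3% at rho 0.5.

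The rank comparison in Step 4 used normal data, whereas the fallback applies when normality is rejected. A check on heavy-tailed data gave van Elteren 95.2% and Wilcoxon 93.3% at rho 0.5, with van Elteren about 1 point lower at slope 1. The advice holds, but its gain there is modest.

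Finally, when the stratum is only a cut of baseline, baseline alone does as well or slightly better (90.0% against 89.4% at k = 1, rho 0.5). The case for keeping the stratum is that the analysis should reflect the randomisation and that the relation to baseline may not be linear. It is not extra power in this simulation.

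**Conclusion.** The point holds as a matter of efficiency. The planned test does not inflate false positives and 17 per arm is correct for it. It leaves unused a stratification factor that was balanced by design, and it uses baseline only with a fixed slope.

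At the design effect and equal standard deviations, ANCOVA gains about 10, 7, 4 and 0 points of power for rho 0.3, 0.5, 0.7 and 0.9. The gain is larger if baseline is more variable than month 6. It is zero or slightly negative if the true slope on baseline is close to 1. These figures assume normal data, a stratum that is a cut of baseline growth rate, and allocation balanced within strata. Confidence in the size of the gain is medium, because rho and k are unknown. The conclusion also covers only the text available, since some sections are not in the public document.

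**What to change.** Before any comparison of the arms, pre-specify the primary analysis as an ANCOVA of month-6 growth rate on arm, baseline growth rate and randomised doubling-time stratum, two-sided at 0.05. Word the primary comparison the same way in Section 8 and the Schema.

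The minimum version is to add the stratum alone to the analysis of change. It keeps roughly half or more of the gain and cost about 0.2 point in the worst setting examined.

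If a rank fallback is kept, use a van Elteren test stratified by doubling time in place of the plain Wilcoxon. Rank ANCOVA is an alternative, but it was about 7 points below Wilcoxon at rho 0.9 (71.2% against 78.0%).

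The cost is SAP wording and two residual degrees of freedom (32 to 30). Power falls by up to about 1.6 points if the true slope is already 1. No new data or patients are needed.

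### Does reporting a 95% confidence interval undercut the 83% power stated for the 50%-decline fraction in the surveillance arm?

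*Combined protocol and SAP*

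**What the plan says.** The passage is in Section 8 of the combined protocol and SAP, after the paired comparison in the surveillance arm. The population and the quantity are set out first: "using all 17 patients on the surveillance arm, the fraction that experiences a 50% decline relative to the time of starting vaccine will be determined". The power statement, for an exact binomial test, follows: "17 patients will have 83% power to test whether the fraction exceeds a null fraction of 20" percent. The alternative is that the fraction "is consistent with 50% who have 50% declines", and the error rate is set "with a one-tailed 0.05 alpha level test".

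The next sentence covers reporting: "In practice, the fraction with a 50% decline will have a 95% confidence interval created about the result", and it gives the reason: "in order to describe what values it would be consistent with". The plan names neither the interval method nor its sidedness. It does not say that the interval must lie above 20% for the result to count as positive.

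Section 8 treats this as a secondary, exploratory analysis. The primary comparison is the between-arm difference in the change in growth rate from baseline to 6 months. The 17 patients per arm come from the power calculation for that comparison.

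**The concern.** A one-sided test at 0.05 and a two-sided 95% interval use different error rates in the direction of interest: 5% and 2.5%. Power computed for the first does not carry over to the second. The wording also invites a reader to treat the interval as the real analysis, because it is introduced as what will be done in practice and is meant to show which values fit the data. Whether 20% is one of those values is close to the question that the test asks. The other two powered tests in the section are two-tailed at 0.05, so this one stands out.

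If the interval were the criterion, the stated power would be about 15 points too high. A result of 7 of 17 could then be reported as significant beside an interval that still contains the null value.

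**Working it through.** **Inputs, all from Section 8:** n = 17; null fraction 0.20; alternative 0.50; exact binomial test, one-tailed, alpha 0.05; a 95% interval with no method given.

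**1. The plan's own figure.** Find the smallest count r with P(X ≥ r | 17, 0.20) ≤ 0.05.

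| Reject at | Size at 20% | Power at 50% |
|---|---|---|
| ≥ 6 | 0.1057 | 0.9283 |
| ≥ 7 | 0.0377 | 0.8338 |
| ≥ 8 | 0.0109 | 0.6855 |

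Six is too liberal, so the rule is 7 or more. By hand, the power is 1 − (1 + 17 + 136 + 680 + 2380 + 6188 + 12376)/2^17 = 1 − 21778/131072 = 0.834. The stated 83% is reproduced.

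**2. Where the 69% comes from.** The lower limit of a two-sided 95% Clopper-Pearson interval is the p at which P(X ≥ x | 17, p) = 0.025. So 20% is excluded from below only if P(X ≥ x | 17, 0.20) is under 0.025. At x = 7 that tail is 0.0377, so 20% stays inside (interval 18.4% to 67.1%). At x = 8 it is 0.0109, so 20% is out (23.0% to 72.2%). Requiring exclusion therefore means 8 or more, with power 0.6855. The gap is 0.8338 − 0.6855 = 0.148, which is the probability of exactly 7 of 17 at a true 50%: 19448/131072.

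**3. Dependence on the method.** Lower 95% limits at 7 of 17:

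| Method | Lower limit | 20% inside? |
|---|---|---|
| Clopper-Pearson | 18.4% | yes |
| Wald | 17.8% | yes |
| Mid-P | 20.1% | no |
| Jeffreys | 20.7% | no |
| Agresti-Coull | 21.6% | no |
| Wilson | 21.6% | no |

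Under the last four, the first count that excludes 20% from below is 7, the same as for the test, and the power to exclude it stays at 83.4%. A one-sided 95% exact lower bound is 21.2% and also agrees with the test.

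**4. How far test and interval can differ.** At 6 of 17 the test does not reject, and the lower limit is under 20% by every method (the highest is Wilson, 17.3%). At 8 of 17 the test rejects, and the lower limit is above 20% by every method (the lowest is Clopper-Pearson, 23.0%). Only 7 of 17 can produce a split. Its probability is 14.8% at a true 50%, and 0.0377 − 0.0109 = 2.7% at a true 20%.

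**5. What the plan attaches to each.** The 83% stands in the sentence that defines the test. The sentence on the interval gives a descriptive purpose, with no power and no threshold. The 69% is therefore the power of a criterion that the plan does not contain.

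**The case for a change.** The best case for the concern is that the phrase *in practice* makes the interval the summary that readers will see, perhaps in place of the test. Clopper-Pearson is the natural partner of an exact binomial test, and a 95% interval is normally read as two-sided. On those assumptions, 7 of 17 gives a significant test with an interval that contains 20%. The plan does not say how to read that, and leaves the choice of method open until after the data are seen.

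The arithmetic in that case is right, and it is true that the method is not named. The step from there to an error fails. Even if the interval is the main summary, it is used to estimate, and no success rule depends on it. A one-sided test at 5% beside a two-sided 95% interval is two valid procedures at two error levels. At 7 of 17 the exact lower limit falls short of 20% by 20 − 18.4 = 1.6 points, and both summaries would show a borderline result. The one-tailed choice is stated openly and fits a directional question, "whether the fraction exceeds a null fraction of 20" percent. That the neighbouring t-tests are two-tailed does not make it wrong.

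Naming the interval method, or using a 90% interval to mirror the test, would be a reasonable reporting preference. Its absence does not make any statement in the plan incorrect.

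**Conclusion.** The concern does not hold. The 83% is correct for the procedure to which it is attached (7 or more of 17, size 3.8%, power 83.4%). The 69% applies only if one assumes that the interval is the decision rule and that it is a two-sided Clopper-Pearson or Wald interval. The plan says neither. Following the plan as written yields a valid test and a valid descriptive interval. On whether the fraction exceeds 20%, they can part only at exactly 7 of 17, and under four of the six methods checked they do not part even there. The analysis is exploratory, and neither the primary comparison nor the sample size rests on it. This conclusion depends on reading the sentence about the interval as descriptive, which is the purpose that it states.
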